Small for Gestational Age (SGA) Infants	Defined as live born infants who are ≤10 th centile on birth weight for infant sex and gestational age will be considered small for gestational age. The U.S. Centers for Disease Control and Prevention (NCHS) [CDC, 2000] growth charts will be used for full term infants, and the Olsen growth charts will be used for preterm infants [Olsen, 2010]. The outcome of birthweight is reported by the mother and validated through the medical record.	live born infants	Excluded due to inherent higher risk of reduced birth size in multiples	At birth	3 months prior to LMP and/or at any time in pregnancy ³	Cohort 1: SGA among live born infants with exposure at any time in pregnancy ³ ; Cohort 2: SGA among live born infants, with no exposure at any time in pregnancy ³

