	
minor structural defects: "hair pattern unruly", "prominent nasal bridge", and "clinodactyly 5th finger bilateral", this would constitute one specific pattern of minor structural defects. For each specific pattern identified in Cohort 1, infants in Cohorts 2 who have the same specific pattern(s) are selected to comprise the numerator for those cohorts. In infants who have more than one specific patterns of at least 3 minor structural defects, each specific pattern will qualify as its own endpoint; therefore, the infant would be counted more than once.
					
infants, with ≥ 3 minor birth defects of any type identified, with no exposure at any time in pregnancy³;

Post-natal growth deficiency
	
Defined as postnatal size at approximately 1 year of age (weight, length or head circumference) less than or equal to the 10th percentile for sex and age using National Center for Health Statistics (NCHS) pediatric growth curves, and adjusted postnatal age for premature infants if the postnatal measurement is obtained at less than 1 year of age. [CDC, 2000].
	
Live born infants
	
Excluded due to inherent higher risk of reduced birth size in multiple
	
From birth up to 1 year of age
	
3months prior to LMP and/or at any time in pregnancy³
	
Cohort 1: Post-natal growth deficiency identified up to 1 year of age among live born infants with exposure at any time in pregnancy³
 
Cohort 2: Post-natal growth deficiency identified up to 1 year of age among live born infants, with no exposure at any time in pregnancy³

Developmental concerns
	
Defined as an abnormal score within the scoring guidelines of the Ages and Stages Questionnaire (ASQ) (Squires, 2009). The ASQ is administered at 12 months of age as a screening tool for developmental milestones by parent report. The ASQ-3 will be sent electronically to the participant or, if the participant prefers, a hard copy questionnaire will be mailed for completion.
	
Live born infants
	
Included each counted separately
	
At 1 year of age
	
3months prior to LMP and/or at any time in pregnancy³
	
Cohort 1:Developmental concerns identified at 1 year of age among live born infants, with pregnancy exposure at any time in pregnancy³;
 
Cohort 2: Developmental concerns identified at 1 year of age among live born infants, with no exposure at any time in pregnancy³

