Variable	Cohort 1 Belimumab- exposed	Cohort 2 Disease comparison	Case-Series Belimumab- exposed (non- cohort)	Data Collection Time Period
Maternal Interviews⁶				
Belimumab exposure timing	√		√	At every interview
Belimumab dose	√		√	At every interview
Belimumab duration	√		√	At every interview
Pregnancy Outcomes				
Any birth defects	√	√	√	At every interview
Other pregnancy outcomes ⁴	√	√	√	At outcome interview
Infant Outcomes (up to 1 year of age)				
Infant size	√	√	√	At outcome interview
Serious infections	√	√	√	At outcome interview
Developmental concerns ⁸	√	√	√	1 year of age
Potential confounders/effect modifiers				
Maternal/paternal characteristics	√	√	√	At enrollment interview
Self-reported disease severity	√	√	√	At every interview
Previous pregnancy and delivery birth defect history	√	√	√	At enrollment interview
Maternal conditions	√	√	√	At every interview
Other maternal exposures/concomitant medications ¹	√	√	√	At every interview
Maternal lifestyle habits	√	√	√	At every interview
Prenatal testing	√	√	√	At every interview
Pregnancy complications	√	√	√	At every interview
Infant complications and pediatric exposures	√	√	√	At outcome interview
Medical Record Abstraction^{2,7}				
SLE diagnosis validation ⁵	√	√	√	Medical history
Pregnancy validation	√	√	√	Medical history
Belimumab Exposure				
Exposure timing, dose, duration validation	√		√	Preconception to pregnancy outcome
Pregnancy Outcomes				
Major birth defects ^{3,9}	√	√	√	LMP to infant 1 year of age
Other pregnancy outcome validation ⁴	√	√	√	LMP to pregnancy outcome
Infant Outcomes (up to 1 year of age)				
Birth and postnatal growth	√	√	√	Birth to 1 year of age

Variable	Cohort 1 Belimumab- exposed	Cohort 2 Disease comparison	Case-Series Belimumab- exposed (non- cohort)	Data Collection Time Period
Serious infections	√	√	√	Birth to 1 year of age
Minor birth defect patterns ^{3,9}	√	√	√	Birth to time of dysmorphology examination
Potential confounders/effect modifiers				
Clinically assessed disease severity	√	√	√	Preconception to pregnancy outcome dependent on last clinical assessment
Previous pregnancy, delivery birth defect history validation	√	√	√	Medical history
Maternal conditions validation	√	√	√	Medical history
Maternal exposure/concomitant medications ¹ validation	√	√	√	Preconception to pregnancy outcome or within 2 years of LMP for specific exposures
Prenatal testing validation	√	√	√	LMP to pregnancy outcome
Infant complications and pediatric exposures	√	√	√	Birth to 1 year of age

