Endpoints relevant to SGA at birth and postnatal growth deficiency at about 1 year of age in weight, height and head circumference (excluding multiple births) are all binary endpoints. The analysis of each of these outcomes will be similar to the analysis of the primary outcome.

Multiple births will be included in the analyses of minor structural defects, developmental concerns and serious infections. The outcome variables thus contain likely correlated data, and the generalized estimating equations (GEE) approach will be used to estimate the crude RR with 95% CI. The causal effect will be estimated similar to the primary outcome, but in place of logistic regression it will be GEE with the logistic link function. The CIs are obtained by 10,000 bootstraps, where the mothers (not infants) will be resampled with replacement.

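### Birth size and 1-year growth are analysed only as yes/no at the 10th centile although the measured values are collected; adding a z-score comparison would recover substantial power for small to moderate shifts

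*Protocol*

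**What the plan says.** Table 2 (Protocol 8.3.2) defines SGA by a cut at the 10th centile: an infant at or below that "centile on birth weight for infant sex and gestational age will be considered small for gestational age". Postnatal growth deficiency is weight, length or head circumference at about 1 year that is "less than or equal to the 10th percentile for sex and age using National Center for Health Statistics (NCHS) pediatric growth curves". Both exclude multiple births.

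Section 8.7.1 then says that SGA and 1-year growth "in weight, height and head circumference (excluding multiple births) are all binary endpoints", and adds: "The analysis of each of these outcomes will be similar to the analysis of the primary outcome". That means a crude RR with 95% CI, followed by propensity-score weighting with a robust variance, and outcome regression with standardisation as a secondary analysis.

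The measurements are gathered in both cohorts. On birth weight, Table 2 says: "The outcome of birthweight is reported by the mother and validated through the medical record". Table 3 (8.4) lists infant size at the outcome interview and, among the items abstracted from records up to 1 year of age, "Birth and postnatal growth".

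The protocol plans no comparison of measured values or z-scores. Section 8.7.2 (exploratory and sensitivity analyses) covers only major birth defects, and 8.7.3 ties the final analyses to the methods of 8.7.1 and 8.7.2. Section 8.5 gives detectable effects for major birth defects and spontaneous abortion, but none for growth.

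**The concern.** Birth weight and 1-year weight, length and head circumference are continuous. Reducing each to one side or the other of the 10th centile discards how far an infant lies from the cut, and with it part of the information on whether the exposed distribution has moved down. Section 8.5 describes signal detection, and 8.9 concedes limited power and poor enrolment in the previous belimumab registry. In that setting, information already held is the cheapest precision available. What is at stake is whether a small to moderate downward shift in growth would show, and how much a non-significant SGA or growth RR can tell the reader.

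This is not a detail left to the SAP. The protocol itself fixes the endpoint type as binary.

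**Working it through.** **Inputs from the protocol.** Two-sided 5% level. Either 160 (conservative) or 170 (expected) pregnancies with at least one live-born infant per cohort (8.5). These counts include multiples and do not allow for missing growth records, so 160 is used as an upper figure under the conservative scenario and 140 as an assumed lower one.

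**Assumptions, because the protocol gives no value.** Normal z-scores with equal SD; the exposed distribution shifted down uniformly by d SD; a proportion p0 of comparators at or below the cut, taken as 10, 15, 20 and 25%. Weighting is ignored.

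**Reproducing the plan's own binary figures first.** Let p̄ = (p0 + p1)/2. The pooled-variance two-proportion formula, equal to the score test at a null ratio of 1, is

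power = Φ{ [ |p1 − p0|·√n − 1.96·√(2p̄(1−p̄)) ] / √( p0(1−p0) + p1(1−p1) ) }.

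Solved for 80% power it gives:
- n = 160: RR 1.94 at a 13% background and 2.84 at 5% (stated 1.9 and 2.8);
- n = 180: RR 2.06 at a 10% background (stated 2.1).

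The formula therefore matches these stated figures to the one decimal printed.

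**Binary power for a shift d.** The exposed proportion is p1 = Φ(Φ⁻¹(p0) + d). For p0 = 10% and d = 0.30:
- p1 = 16.3%, RR = 1.63, p̄ = 0.1316;
- |p1 − p0|·√160 = 0.0632 × 12.65 = 0.799;
- 1.96·√(2p̄(1−p̄)) = 1.96 × 0.478 = 0.937;
- denominator = √(0.0900 + 0.1366) = 0.476;
- power = Φ((0.799 − 0.937)/0.476) = Φ(−0.29) = 39%.

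**z-score power for the same shift.** Power ≈ Φ(d·√(n/2) − 1.96) = Φ(0.30 × 8.94 − 1.96) = Φ(0.72), or 76-77%. The two-sample t-test (noncentral t) gives 76%. A simulation of 20,000 studies gave 39% for the binary test and 77% for the z-score.

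**Over the assumed ranges:**

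| n per cohort | Shift | Binary power at p0 = 10 / 15 / 20 / 25% | z-score power |
|---|---|---|---|
| 160 | 0.20 SD | 19 / 23 / 25 / 27% | 43% |
| 160 | 0.25 SD | 28 / 33 / 37 / 39% | 61% |
| 160 | 0.30 SD | 39 / 45 / 50 / 53% | 76% |
| 160 | 0.40 SD | 62 / 70 / 75 / 78% | 95% |
| 160 | 0.50 SD | 82 / 88 / 91 / 93% | 99% |
| 140 | 0.30 SD | 35 / 40 / 45 / 47% | 71% |

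**Detectable shift at 80% power, n = 160.** Binary: 0.49 SD at p0 = 10% (RR 2.13) and 0.42 SD at p0 = 20% (RR 1.69). z-score: 0.31 SD.

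**Infants needed per cohort for 80% power at 0.30 SD, p0 = 10%.** 449 binary against 175 continuous, a ratio of 449/175 = 2.6.

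**The case against.** The strongest reply is that nothing here is an error. The objectives name SGA infants and postnatal growth deficiencies, which are threshold conditions that clinicians recognise, and 8.7.1 analyses what the objectives name. A mean shift is a different question. The detectable RR of about 1.7-2.1 (p0 of 20% and 10%) is no worse than what the protocol accepts elsewhere: 1.9-2.8 for major birth defects and 2.1 for spontaneous abortion. A SAP could add a continuous analysis. This stands as a reason to keep the binary endpoints and to treat the point as an improvement. It does not remove the gap, because the protocol declares these endpoints binary and plans nothing else for data it already collects.

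A reader might infer that the cut removes most of the power. The figures do not support that. At 0.3 SD the loss is between (76 − 53)/76 = 30% and (76 − 39)/76 = 49% of the z-score power; at 0.4 SD it is 18-35%. It exceeds half only at 0.2 SD with a 10% comparator rate ((43 − 19)/43 = 56%), where the z-score analysis would itself miss the effect more often than not.

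A reader might also infer that a moderate growth effect would usually be missed. That depends on the shift and the rate. At 0.3 SD with 20-25% of comparators below the cut it is about an even chance, and at 0.4 SD or more the binary test usually detects the shift. An effect confined to the lower tail would lose less by the cut than a uniform shift.

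Three further cautions stand. The 160 counts pregnancies including multiples, and growth data depend on complete records (Table 3 footnote; 8.9), so the usable number is smaller. Nothing in the protocol says that a null result will be taken as reassurance on growth, and the CIs will show the imprecision. A mean alone could hide a lower-tail excess. In addition, SGA uses one chart for term and another for preterm infants, while section 6.1 puts preterm delivery in SLE at about 40%, so a pooled birth-weight z-score mixes two references.

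**Conclusion.** The point holds as a worthwhile improvement to secondary analyses, not as a contradiction or a wrong endpoint. For shifts of about 0.2-0.3 SD, and with at most 160 infants per cohort, analysing the z-score raises power from 19-27% to 43% (0.2 SD) and from 39-53% to about 76% (0.3 SD). With 140 infants, the 0.3 SD figures are 35-47% and 71%. At 0.4 SD the gain is 17-33 percentage points, but the binary test already has 62-78% power; at 0.5 SD little is left to gain.

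These sizes rest on assumed normal z-scores with equal SD, a uniform shift and comparator rates of 10-25%, none of which the protocol supplies. Weighting would be expected to lower both powers. The importance is moderate: the endpoints are secondary, but the data are already collected.

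**What to change.** Keep the 10th-centile proportions and RRs as the defined secondary endpoints. Add to 8.7.1 a supporting analysis, in singletons, of the between-cohort mean difference with 95% CI in:
- birth-weight z-score for sex and gestational age;
- 1-year weight, length and head-circumference z-scores for sex and age.

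Use the propensity weighting and robust variance already planned. State that any conclusion on growth will be read from both the z-score CI and the CI of the 10th-centile RR, and not from the mean alone. Because term and preterm birth weights use different reference charts, check the birth-weight result by term/preterm status.

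The cost is a few sentences in 8.7.1, some extra table rows and four more secondary estimates. A mean z-score difference is less familiar clinically than SGA, which is a further reason to report the two together. No new data collection and no change to the primary endpoint are needed.

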8.7.2. Exploratory/Sensitivity analyses

For the primary outcome of major structural birth defects,

- exploratory analyses addressing potential effect modifiers such as disease severity will be conducted. Specifically, confounder adjustment might be carried out both including and excluding these disease severity measures;
- sub-analyses using graphical presentation based on gestational timing as well as dose of exposure to belimumab will be performed.
- a sensitivity analysis will be performed excluding those defects thought to be of chromosomal or genetic origin.
- exposure to a known human teratogen is already included in the list of potential confounders (within maternal exposure and lifestyle habits in Section 8.3.3). However, in the case where there are insufficient number of events to consider regression adjustment, a sensitivity analysis will be performed excluding participants with exposure to known teratogens to address this potential confounder.
- a sensitivity analysis will be performed stratified on any abnormal finding (yes/no) among those with prenatal testing prior to enrollment.

- exposure in the 2nd and 3rd trimesters will be considered for those selected major birth defects that are potentially biologically plausibly related to later pregnancy exposure, e.g., craniosynostosis” [Jones, 2013]

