8.3.3. Confounders and effect modifiers

The potential confounders/effect modifiers listed below will be considered in multivariable analyses, where possible, as well as others that are relevant to each of the study outcomes:

- Maternal and paternal age
- Previous pregnancy history: gravidity and parity, previous spontaneous abortions and elective terminations
- Maternal and paternal race/ethnicity, education, occupation, socioeconomic status
- Pre-pregnancy body mass index
- Previous preterm delivery
- Previous child with a birth defect
- Maternal conditions: e.g., depression, diabetes
- Maternal exposures: gestational timing and dose of all over-the-counter and prescription medications, including all medications for the treatment of SLE used during pregnancy; vitamin and mineral supplements, herbal products; illnesses; fever; vaccinations
- Prenatal testing: ultrasound and other prenatal tests; timing in gestation and results
- Pregnancy complications: e.g., pregnancy induced hypertension, gestational diabetes, prolonged labor (definitions included in Section 14 Glossary)
- Maternal lifestyle habits: cigarette smoking, alcohol consumption and illicit drug use
- SLE disease severity assessment (see ANNEX 1 [Section 15.1] for details)
- Relevant lab values where available (e.g., CBC with differential, urinalysis: protein, red blood cell (RBC), white blood cell (WBC), casts, urine protein:creatinine ratio, dsDNA antibody, anti-phospholipids C3 and C4)
- Infant complications: e.g., hospitalizations, congenital heart block,
- Relevant pediatric exposure: any vaccines administered, infections requiring hospitalization in first year of life, breastfeeding status

Methods for identifying and controlling for these confounders and/or effect modifiers are described in Section 8.7.1. The SAP will provide greater detail on the definitions of, the identification of and the controlling for confounders and/or effect modifiers.

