8.7. Data analysis

8.7.1. Essential analysis

A stepwise approach will be used for the analysis: The initial analysis will be descriptive and unadjusted. Where numbers permit, multivariable analyses will be conducted for the primary and secondary analyses to adjust for possible confounders.

Statistical methods:

A detailed SAP will be prepared and finalized prior to the conduct of any study analysis. Patient characteristics will be summarized within each cohort for the interim and final reports.

Table 6 summarizes the exposure window for each outcome.

Table 6 Summary of Exposure Window for Each Outcome

Outcome	Exposure Window
Major Birth Defects	3 months prior to LMP to the end of the 1 st trimester
Minor Birth Defects	3 months prior to LMP to the end of the 1 st trimester
Spontaneous Abortion/Miscarriage	3 months prior to LMP to prior to 20.0 weeks' gestation
Preterm Delivery	3 months prior to LMP to prior to 37.0 weeks' gestation
Other Outcomes	3 months prior to LMP to the end of the pregnancy

For the primary endpoint, the exposure of interest is belimumab exposure in the pre-conception/first trimester period. For this study, this exposure is defined as any dose from 3 months prior to the 1st day of LMP and up to 13 weeks after the 1st day of the LMP. The primary comparison will be on the rate of major birth defects between Cohort 1 and Cohort 2 among pregnancies resulting in at least one live born infant. A point estimate of the crude (i.e. unadjusted) RR of Cohort 1 versus Cohort 2, as well as its 95% confidence intervals (CIs) will be computed.

The comparison will also be carried out within each of two strata, according to whether the woman had prenatal diagnostic testing, such as level II ultrasound, amniocentesis or chorionic villus sampling, prior to enrollment in the study or not.

The same analysis will be repeated using the second numerator and denominator encompassing pregnancies ending in at least one live births, stillbirth, spontaneous abortion or elective termination, but excluding those lost-to-follow-up.

Due to the observational nature of the study, the above crude estimate of RR will be further adjusted for potential confounders, provided that there are sufficient number of events. A complete list of potential confounders will be provided in a separate table for each outcome prior to the final analysis, based on scientific knowledge including literature review. In addition, all of the following three criteria will be applied in

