accordance with the definition of confounders, and variables will be considered in a step-wise approach where any of these criteria are met: 1) by assessing each considered variable in a logistic regression model containing exposure and the outcome to determine if inclusion of that single covariate changes the estimate of the odds ratio for exposure by 10% or more; 2) standardized mean differences (SMD) greater than 0.1; 3) association with the outcome with p-value <0.2 in the unexposed group. Care will be taken not to include those variables that are strongly associated with the exposure but only weakly associated with the outcome.

The confounders identified above may be used to build the propensity score (PS) for exposure [Rosenbaum, 2002]. R package ‘twang’ or similar R package available at the time of analysis will be used for this purpose, following which SMD will be used to check the balance of the covariates between the cohorts.

The primary analysis will be performed with inverse probability weighting (IPW) using the propensity score. In the IPW approach, we will use stabilized weights that are further trimmed to be between 0.1 and 10 if necessary [Peter, 2015]. The robust sandwich variance estimator will be used following the IPW approach.

A secondary analysis will be conducted using outcome regression, i.e. a logistic regression model will be fitted with major structural defect (Y) as outcome, and exposure (A) and propensity score (L) as regressors. Standardization will be performed to obtain the estimated causal risk ratio [Hernán, 2019], which has the interpretation as the marginal or population averaged risk ratio. The CIs are obtained by 10,000 bootstraps.

For the secondary endpoints

The ideal pregnancy cohort would enroll women at conception, before any outcome, and then follow them for years after delivery. However, this is unrealistic for logistical reasons. Therefore, outcomes that must account for gestational age at enrollment (e.g. SAB) will have left truncation and right censoring. Left truncation occurs because participants enroll after conception and, therefore, after some outcomes may have already occurred. Right censoring occurs when there are enrolled pregnancies with unknown

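### Effect modification by disease severity is assigned a method, adjustment with and without severity, that measures confounding instead (minor)

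*Protocol*

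**What the plan says.** For the primary outcome, the first bullet of Protocol Section 8.7.2 states an aim: "exploratory analyses addressing potential effect modifiers such as disease severity will be conducted". Its next sentence, introduced as the specification of that aim, says that "confounder adjustment might be carried out both including and excluding these disease severity measures". The bullet names no other method.

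Section 8.3.3 lists SLE disease severity among the potential confounders and effect modifiers and says that "Methods for identifying and controlling for these confounders and/or effect modifiers are described in Section 8.7.1". It adds that "The SAP will provide greater detail on the definitions of, the identification of and the controlling for confounders and/or effect modifiers".

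Section 8.7.1 describes confounder selection, propensity-score weighting, and an outcome regression with exposure and propensity score as regressors. It has neither an exposure-by-severity term nor severity strata. Its one stratified comparison is on another factor: "The comparison will also be carried out within each of two strata, according to whether the woman had prenatal diagnostic testing". The stratified sensitivity analysis in Section 8.7.2 is by abnormal prenatal finding.

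**The concern.** Effect modification asks whether the RR for belimumab differs between women with milder and more severe lupus. Answering it needs an estimate at each severity level or a term for the difference between levels. Adding severity to an adjustment set, or leaving it out, answers another question: how much of the averaged RR reflects different severity in the two cohorts.

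The protocol treats the with/without contrast that way elsewhere. One of its criteria for a confounder in Section 8.7.1 is whether "inclusion of that single covariate changes the estimate of the odds ratio for exposure by 10% or more". Section 8.7.2 applies the same kind of contrast under the label of effect modification.

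Two misreadings could follow. A shift between the two RRs could be reported as a difference in effect by severity, and agreement between them could be reported as evidence that the effect is uniform. Section 8.7.3 says the final analyses follow Sections 8.7.1 and 8.7.2, and Section 8.9 lists proper attention to effect modification as a strength of the design, so the label matters even for exploratory output.

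**Working it through.** The protocol gives no figure for this analysis, so there is none to reproduce. The check is whether the named contrast responds to effect modification, using expected risks in two constructed situations. All inputs are assumptions except the 5% risk in A, which is the lower SLE background rate in Table 4.

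**Formulas.** Let h1 and h0 be the share with high severity in the exposed and unexposed cohorts, pL and pH the unexposed risks at low and high severity, and RL and RH the true RRs.

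- RR without severity = [(1−h1)·pL·RL + h1·pH·RH] / [(1−h0)·pL + h0·pH]
- RR with severity, standardized to the pooled share s = (h1+h0)/2 for cohorts of equal size = [(1−s)·pL·RL + s·pH·RH] / [(1−s)·pL + s·pH]

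The second formula is the kind of quantity that weighting or standardization targets. Section 8.7.1 says of its standardized ratio: "which has the interpretation as the marginal or population averaged risk ratio".

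**A. Effect modification, no confounding.** h1 = h0 = 0.5; pL = pH = 0.05; RL = 1.0; RH = 3.0.

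- Without severity: (0.5×0.05×1.0 + 0.5×0.05×3.0) / 0.05 = 0.100/0.050 = 2.00
- With severity (s = 0.5): 0.100/0.050 = 2.00
- Change: 0%. True ratio of stratum RRs: 3.0.

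**B. Confounding, no effect modification.** h1 = 0.7; h0 = 0.3; pL = 0.03; pH = 0.07; RL = RH = 1.5.

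- Without severity: (0.3×0.03×1.5 + 0.7×0.07×1.5) / (0.7×0.03 + 0.3×0.07) = 0.087/0.042 = 2.07
- With severity (s = 0.5): (0.5×0.045 + 0.5×0.105) / (0.5×0.03 + 0.5×0.07) = 0.075/0.050 = 1.50
- Change: 1.50/2.071 − 1 = −28%. True ratio of stratum RRs: 1.0.

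The contrast is silent in A, where the effect differs threefold, and moves in B, where it does not differ. Stratum-specific RRs would show the right pattern in both.

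**How much severity-specific estimates could show.** Section 8.5 expects 160 pregnancies with a live birth per cohort (conservative case) and Table 4 uses 5% to 13% as the SLE background rate. Assume an even severity split (m = 80 per cell) and equal risk p in all four cells.

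- Events per cell = m·p: 80×0.05 = 4.0; 80×0.13 = 10.4
- SE of the log ratio of the two RRs = √[4(1−p)/(m·p)]: √(3.8/4.0) = 0.975; √(3.48/10.4) = 0.578
- Ratio of RRs detectable with 80% power, two-sided 5% = exp[(1.960+0.842)×SE]: about 15 at 5%; about 5 at 13%
- With 170 per cohort: about 14 and 4.8

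These are large-sample approximations and are rough at 4 events per cell.

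**The case against.** The strongest reply is that the bullet is exploratory, speaks of analyses in the plural, and says only that the with/without adjustment might be done. It does not exclude strata or an interaction term, and Section 8.3.3 defers detail on effect modifiers to the SAP, which was not available here. This stands in part. A reader might infer that the study will produce no analysis of effect modification by severity; the documents do not support that, and the absence of severity-specific RRs from the protocol is not in itself a fault. What remains is that the protocol itself attaches a method to an aim it cannot serve, and an SAP that elaborated that method would carry the mismatch forward.

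A reader might also infer that the RR without severity omits the main confounder and invites selective quotation. The protocol does not rank severity as a confounder for birth defects: Section 6.1 ties lupus activity to fetal loss and preterm delivery, and Section 8.1 treats severity as a confounder across outcomes generally. The adjusted primary analysis is fixed as inverse probability weighting, and a crude RR, which already omits severity, is reported anyway.

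Nor do the documents support a rule that severity must always be adjusted for. Section 8.7.1 cautions against variables strongly related to exposure but only weakly to outcome, and severity may be one for this endpoint. Severity is also recorded throughout pregnancy (Table 3), so later values may reflect treatment. Both are good reasons to fit the model both ways, as a sensitivity analysis for confounding.

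Finally, severity-specific RRs would be imprecise. That is correct and limits what the remedy can deliver.

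**Conclusion.** The point holds as a minor one. The only method Section 8.7.2 names for effect modification by severity measures confounding by severity. In the constructed cases it changed by 0% when the stratum RRs were 1.0 and 3.0, and by −28% when both were 1.5. Those sizes rest on assumed inputs and are not predictions for this study; the conclusion that the contrast does not isolate a difference in effect does not depend on them.

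The primary comparison, its weighting and the sample size are unaffected. With about 4 to 10 events per cell under an even split and equal risks, severity-specific results could only describe.

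**What to change.** - **Relabel.** In Section 8.7.2, call adjustment with and without severity a sensitivity analysis for confounding by severity, separate from effect modification. Whether severity enters a given adjustment set stays with the selection rules in Section 8.7.1.
- **Give effect modification its own method.** Report RRs with 95% CIs within pre-defined severity levels, or fit an exposure-by-severity term, labelled exploratory and descriptive and done where events allow.
- **State which severity measure is used.** Take the earliest available, preferably pre-exposure or preconception from medical records. Exposure counts from 3 months before LMP and enrollment averages 7–10 weeks after it, so severity at enrollment may already reflect treatment.

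The cost is a wording change and a few extra exploratory table rows with wide intervals. Table 3 marks self-reported and clinically assessed severity for both cohorts, so no new collection is planned for. Two limits apply: record-based values depend on how complete the records are, and Section 8.4 describes the severity interview for women exposed to belimumab or other SLE medications. It should be confirmed that untreated comparison women are covered.
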